14.2 Palatability (taste and ability to consume medicine) Questionnaire

Directions

The following questions are about the medicine your child takes for iron overload (too much iron in the body). Please read each one and answer by yourself. There is no right or wrong answer. All of your answers will remain confidential.

Please answer each question about the medicine your child took for iron overload in the past week:

Items

1. Please choose the face that best describes your child's reaction to the taste of the medicine for iron overload immediately after putting it in his/her mouth in the past week.

1

2

3

4

5

Very Good

Good

Neither Good nor Bad

Bad

Very Bad

2. Please choose the face that best describes your child's reaction to the aftertaste of the medicine after swallowing his/her medicine for iron overload in the past week.

1

2

3

4

5

Very Good

Good

Neither Good nor Bad

Bad

Very Bad

3. Using the answers listed below, which answer best, describes what happened after your child took his/her medicine for iron overload in the past week?

- Swallowed and retained ALL of the medicine
- Spat out SOME of the medicine
- Spat out ALL of the medicine and swallowed none of it
- Vomited within 30 minutes after swallowing the medicine

4. How would you describe the amount of liquid that your child took with his/her medicine for iron overload in the past week?

- Not enough liquid
- Just enough liquid
- Too much liquid

14.3 GI Symptom Questionnaire

Directions

Please read each symptom carefully. Indicate how often your child had each symptom **over the past week.**

Please answer all of the following questions about your child's GI symptoms after taking his/her medication for iron overload.

Items

1. Pain in his/her belly

- Always
- Most of the time
- Sometimes
- Rarely
- Never

2. Nausea (feeling like he/she might throw up)

- Always
- Most of the time
- Sometimes
- Rarely
- Never

3. Vomiting (throwing up)

- Always
- Most of the time
- Sometimes
- Rarely
- Never

4. Constipation

- Always
- Most of the time
- Sometimes
- Rarely
- Never

5. Diarrhea

- Always
- Most of the time
- Sometimes
- Rarely
- Never

6. How many bowel movements did your child have in the past week?

- 0 (none)
- 1
- 2
- 3
- 4
- 5-10
- 11 or more

14.4 Deferasirox FCT Weight Dose Table

Body weight ranges per dosing group (kg)									# of Tablets to dispense		
3.5 mg/kg/day [kg]	7 mg/kg/day [kg]	10.5 mg/kg/day [kg]	14 mg/kg/day [kg]	17.5 mg/kg/day [kg]	21 mg/kg/day [kg]	24.5 mg/kg/day [kg]	28 mg/kg/day [kg]		90 mg	180 mg	360 mg
19 - 38	10 - 19	7 - 12	5 - 9	5 - 7	5 - 6	5		1			
39 - 64	20 - 32	13 - 21	10 - 16	8 - 12	7 - 10	6 - 9	5 - 8		1		
65 - 90	33 - 45	22 - 30	17 - 22	13 - 18	11 - 15	10 - 12	9 - 11	1	1		
91 - 115	46 - 57	31 - 38	23 - 28	19 - 23	16 - 19	13 - 16	12 - 14			1	
116 - 140	58 - 70	39 - 47	29 - 35	24 - 28	20 - 23	17 - 20	15 - 17	1		1	
	71 - 83	48 - 55	36 - 41	29 - 33	24 - 27	21 - 23	18 - 20		1	1	
	84 - 96	56 - 64	42 - 48	34 - 38	28 - 32	24 - 27	21 - 24	1	1	1	
	97 - 109	65 - 72	49 - 54	39 - 43	33 - 36	28 - 31	25 - 27			2	
	110 - 122	73 - 81	55 - 61	44 - 48	37 - 40	32 - 34	28 - 30	1		2	
	123 - 135	82 - 90	62 - 67	49 - 54	41 - 45	35 - 38	31 - 33		1	1	2
	136 - 140	91 - 98	68 - 73	55 - 59	46 - 49	39 - 42	34 - 36	1	1	1	2
	99 - 107	74 - 80	60 - 64	50 - 53	43 - 45	37 - 40				3	
	108 - 115	81 - 86	65 - 69	54 - 57	46 - 49	41 - 43		1		3	
	116 - 124	87 - 93	70 - 74	58 - 62	50 - 53	44 - 46			1	1	3
	125 - 132	94 - 99	75 - 79	63 - 66	54 - 56	47 - 49		1	1	1	3
	133 - 140	100 - 106	80 - 84	67 - 70	57 - 60	50 - 52				4	
	107 - 112	85 - 90	71 - 75	61 - 64	53 - 56		1			4	
	113 - 118	91 - 95	76 - 79	65 - 67	57 - 59			1		4	
	119 - 125	96 - 100	80 - 83	68 - 71	60 - 62		1	1		4	
	126 - 131	101 - 105	84 - 87	72 - 75	63 - 65				5		
	132 - 138	106 - 110	88 - 92	76 - 78	66 - 69		1		5		
	139 - 140	111 - 115	93 - 96	79 - 82	70 - 72			1	1	5	
	116 - 120	97 - 100	83 - 86	73 - 75		1	1		5		
	121 - 126	101 - 105	87 - 90	76 - 78					6		
	127 - 131	106 - 109	91 - 93	79 - 81		1			6		
	132 - 136	110 - 113	94 - 97	82 - 85				1	1	6	
	137 - 140	114 - 117	98 - 101	86 - 88		1	1		6		
	118 - 122	102 - 104	89 - 91						7		
	123 - 126	105 - 108	92 - 94		1			1	7		
	127 - 130	109 - 112	95 - 98					1	7		
	131 - 135	113 - 115	99 - 101		1	1			7		
	136 - 139	116 - 119	102 - 104						8		
	140	120 - 123	105 - 107		1			1	8		
	124 - 126	108 - 110						1	8		
	127 - 130	111 - 114		1	1			1	8		
	131 - 134	115 - 117							9		
	135 - 137	118 - 120		1				1	9		
	138 - 140	121 - 123						1	9		
	124 - 126		124 - 126	1	1			1	9		
	127 - 130								10		
	131 - 133				1				10		
	134 - 136							1	10		
	137 - 139				1	1			10		
	140								11		

These dosing tables have been constructed for each dosing group using lower and upper body weight limits of 5 and 140 kg, respectively. This is taking into account that the study will

enroll male or female children, ≥ 2 and < 6 years. For patients with a low body weight (e.g. below 19 kg in the 5 mg/kg/day dosing group) the dosing requirements given will not allow for the use of the smallest strength available. In such cases a written request will be sent to Novartis, to advise on the individual patient enrolment / dose adjustments options.

14.5 Examples of light meals with soft foods

Table 14-1 Examples of light meals with soft foods

Example 1	Amount	kcal	g total fats
Wheat Bread or Toast jams, preserves, all flavors	2 slices 1 Tablespoon	138 109	2 0
Banana	Medium (7-7 7/8" long)	105	0
Orange juice	1 cup	114	0
Skim milk	1 cup	83	0
Total:		549	2

Example 2	Amount	kcal	g total fats
Pita Bread	1 medium (5.25" across) pita	124	1
Hummus or deli chicken/turkey	1 Tablespoon hummus or 2 oz. meat	27	1
Apple	Medium (2.75" across)	72	0
Salsa, red, cooked	6 Tablespoons	26	0
Carrots & celery sticks	4 carrot sticks (3" long) and small 5" stalk of celery	14	0
Total:		263-295	2

Example 3	Amount	kcal	g total fats
Yogurt, fruit, low-fat	6 oz.	173	2
Banana	Medium (7-7 7/8" long)	105	0
Orange juice	1 cup	114	0
Skim milk	1 cup	83	0
Total:		475	2

Example 4	Amount	kcal	g total fats
Vegetable chicken noodle soup, canned	1 cup	70	2
Baked potato, peel not eaten	1 medium (2.25-3" across)	121	0
Skim milk	1 cup	83	0
banana	Medium (7-7 7/8" long)	105	0
Total:		379	2

Example 5	Amount	kcal	g total fats
Egg whites, cooked, no fat added	2 large egg whites	32	0
Salsa, red, cooked	6 Tablespoons	26	0
Wheat Bread or Toast	2 slices	138	2
Jams, preserves, all flavors	1 Tablespoon	109	0
Orange juice	1 cup	114	0
Skim milk	1 cup	83	0
Total:		502	2

Example 6	Amount	kcal	g total fats
chicken, boneless, skinless baked	0.5 cup diced	111	2
salsa, red, cooked	6 Tablespoons	26	0
white rice, cooked, no fat added	0.5 cup	102	0
black beans, canned or cooked from dry, no fat added	0.5 cup	99	0
skim milk	1 cup	83	0
Total:		421	2

Post-Authorization Safety Study (PASS)

Is this a PASS study - If yes, follow instructions below

 Yes No

SD	Standard deviation
SOC	System organ class
TBIL	Total Bilirubin
TLF	Tables, Listings and Figures

UPCR Urine protein and creatinine ratio
SSD Study Specification Document
WHO World health organization

1 Introduction

The purpose of this Statistical Analysis Plan (SAP) is to describe the implementation of the statistical analysis specified in the protocol. Final Clinical Study Report (CSR) will be written based on this SAP. Current SAP is written following finalized protocol version 01 (Amended protocol), disease area standards and deferasirox (film coated tablet (FCT)) project specific standard TFLs. All decisions regarding final analysis, as defined in the SAP document, have been made prior to database lock of the study data.

1.1 Study design

This is an interventional, prospective, single arm, open label, global multi-center, non-randomized study to monitor and assess the safety profile of the crushed deferasirox FCT in pediatric patient's age between ≥ 2 to < 6 years with transfusional hemosiderosis over 24 weeks. The purpose of this study is to address a European Health Authorities (CHMP/PRAC) post-marketing requirement. CHMP/PRAC have requested Novartis for an additional post-authorization safety study to characterize the pediatric safety profile and to provide safety data on selected AEs (esophagitis, stomatitis, mouth ulceration, gastric ulcers, hemorrhage, abdominal pain, diarrhea, nausea, and vomiting).

This study will enroll at least 40 patients worldwide.

The study will include a screening period (from Day 0-14) with two visits at least 7 days apart to assess eligibility of patients that are chelation naïve or on a prior iron chelator treatment other than deferasirox (DFX). Only one screening visit (screening visit 1) will occur for prior DFX treated patients to determine eligibility. Any patients treated with prior chelation therapy except deferasirox will be discontinued to undergo a 5-day washout period before initiation of 24-week treatment period with crushed deferasirox FCT.

Safety assessments will be performed weekly after treatment initiation for the first 4 weeks and thereafter monthly during the study. Monthly serum ferritin values and trends will be used to adapt the treatment of the patients together with safety data. Patients will continue therapy for up to 24 weeks.

There is no interim analysis planned for this study.

1.2 Study objectives and endpoints

The study objectives and endpoints are described in the following table:

Table 1-1 Study objectives and endpoints

Objective	Endpoint
Primary	

To assess the safety of crushed deferasirox FCT with respect to selected gastrointestinal (GI) disorders in pediatric patients aged ≥ 2 to < 6 years with transfusional iron overload up to 24 weeks including 30 days safety follow up	Number and percentage of patients with selected gastrointestinal disorders (esophagitis, stomatitis, mouth ulceration, gastric ulcers, hemorrhage, abdominal pain, diarrhea, nausea, and vomiting) up to 24 weeks including 30 days safety follow-up
Secondary	
Evaluate AEs suspected to be related to the crushed deferasirox FCT	Number and percentage of patients who experienced AEs suspected to be related to study treatment up to 24 weeks including a 30 day follow up overall and by SOC.
To assess the overall safety of crushed FCT of deferasirox	Overall safety up to 24 weeks including 30 days safety follow-up as measured by frequency and severity of adverse events, serious adverse events (SAEs) and AEs leading to discontinuation and absolute change from baseline over time (shift tables will also be provided) for serum creatinine, creatinine clearance, UPCR, total bilirubin, ALP, ALT, AST). Other safety data (e.g., ECGs, vital signs, ocular, auditory examinations) will also be summarized.
To assess the efficacy of deferasirox FCT treatment	Change from baseline over time in SF up to 24 weeks of treatment
To evaluate patient treatment satisfaction, palatability, and GI symptoms with Observer-reported Outcomes (ObsROs)	Domain scores with ObsROs (Modified Satisfaction with Iron Chelation Therapy [mSICT], palatability, and GI symptom) questionnaires

2 Statistical methods

This section contains information that will be used to draft CSR Section 9.7 on statistical analysis.

2.1 Data analysis general information

Data will be analyzed by Novartis Oncology Biostatistics and Statistical programming personnel according to the data analysis described in Section 10 of the ICL670F2429 protocol, which will be available in Appendix 16.1.1 of the Clinical Study Report (CSR). Important information is given in the following sections and details are provided. For the final analysis, SAS version 9.4 or later (upon availability) will be used. As specified in the protocol, the study will continue until last patient received last dose plus 30-days follow-up. This date will be considered as the cut-off date.

Data from all patients who signed the main study informed consent for study participation in centers that participate in this study will be used in the analysis; due to expected small size of enrollment at individual centers, no center effect will be assessed. Each analysis will use all data in the database up to the analysis cutoff date, determined prior to database lock.

All available data from all patients up to the cutoff date will be reported. Data collected after patients' withdrawal of informed consent for further participation in the study will not be reported (except for death date which might be obtained from public records).

2.1.1 General presentation of descriptive summaries

Qualitative data (e.g., gender, race, etc.) will be summarized by frequency count and percentages. Percentages will be calculated using the number of patients in the relevant population as the denominator.

Quantitative data (e.g., age, body weight, etc.) will be summarized by appropriate descriptive statistics (i.e. mean, standard deviation, median, minimum, and maximum). For selected parameters 25th and 75th percentiles will also be presented in box plots.

2.1.2 General definitions

2.1.2.1 Investigational drug and study treatment

Investigational drug will refer to the crushed Deferasirox FCT only. In this document, the term investigational drug will be referred as **study treatment** and will be used throughout this document.

2.1.2.2 Date of first administration of study treatment

The date of first administration of study treatment will be derived as the first date when a nonzero dose of study treatment is administered as per the Dosage Administration CRF. For the sake of simplicity, the date of first administration of study treatment will also be referred as **start of study treatment**.

2.1.2.3 Date of last administration of study treatment

The date of last administration of study treatment is defined as the last date when a nonzero dose of study treatment was administered as per Dose Administration (e)CRF.

2.1.2.4 Screening failure

Screening failures are patients who have been enrolled and failed screening criteria in a study. These patients will never receive investigational drug.

2.1.2.5 Study day

The study day **for safety assessments** (e.g. adverse event onset, laboratory abnormality occurrence, vital sign measurement, dose interruption etc.) and **for efficacy assessment** (e.g.

serum ferritin) and Observer-reported Outcomes will be calculated as the difference between the date of the event (onset date of an event, assessment date etc.) and the start of study treatment plus 1. The first day of study treatment is therefore study day 1 if event will start after start date of study treatment.

Study day=date of event – start date of study treatment+1

For any assessment or events such as baseline disease characteristics or medical history (e.g., time since diagnosis of disease) that is supposed to occur prior to treatment start date, study day will be negative and will be calculated as:

Study Day = Event date -treatment start date.

The study day will be displayed in the data listings.

2.1.2.6 Baseline

For the **safety** and the **efficacy evaluations**, the last available assessment on or before the date of start of study treatment will be defined as baseline. If patients have no value as defined above, the baseline result will be missing.

2.1.2.7 On-treatment assessment/event and observation periods

The overall observation period will be divided into three mutually exclusive segments:

1. **pre-treatment period:** from day of subject's first informed consent to the day before first administration of study treatment
2. **on-treatment period:** from date of first administration of study treatment to 30 days after date of last actual administration of any study treatment (including start and stop date)
3. **post-treatment period:** starting at day 30+1 after last administration of study treatment.

All safety data (including those from the pre-treatment period) will be listed and those collected during the pre-treatment period are to be flagged. If any safety data from the post-treatment period is collected, it will be flagged.

2.2 Analysis sets

The following analysis sets are defined in the study protocol.

2.2.1 Full Analysis Set

The Full Analysis Set (FAS) comprises all patients who received at least one dose of deferasirox FCT during the study.

2.2.2 Safety Analysis Set

The Safety Set includes all patients who received at least one dose of deferasirox FCT during the study. Note that the Safety Set and the FAS will be the same for this single arm phase IV study.

2.2.3 Per-Protocol set

Not applicable

2.2.4 Dose-determining analysis set

Not applicable

2.2.5 Pharmacokinetic analysis set

Not applicable

2.2.6 Other analysis set

Not applicable

2.2.7 Efficacy/evaluable set

Not applicable

2.3 Subgroup of interest

Not Applicable

2.4 Protocol deviations

Frequency counts and percentages of patients with any CSR reportable protocol deviation (selection criteria not met, patient not withdrawn as per protocol, treatment deviation, prohibited concomitant medication, and other (Good Clinical Practice (GCP) deviation) will be tabulated by the deviation type category using FAS.

The full list of protocol deviations is documented in the Study Specification Document (SSD) Module 3. All protocol deviations will be listed.

2.5 Patient disposition, demographics and other baseline characteristics

Screen failures recorded in the end of screening phase disposition will comprise patients who have been enrolled i.e. signed the main ICF and were screened but were not treated. The screening failure disposition table will include:

- Number (%) of screen-failed patients
- Reasons for screening failure

The percentage for the screening phase disposition will be calculated based on the number of patients whose consents are obtained. All screen failure patients with reasons for screen failure will be listed.

Patient disposition will be summarized using the FAS. The disposition table will include:

- Number (%) of treated
- Number (%) discontinued before 24-week schedule visit
- Number (%) of patients who completed the end of treatment
- Primary reason for study treatment phase discontinuation (based on the 'End of Treatment Phase' page)

All demographic data and baseline disease characteristics will be summarized and listed based on the FAS. Categorical data (e.g. gender, age, race, and ethnicity) will be summarized by frequency counts and percentages; the number and percentage of patients with missing data will be provided. Continuous data (e.g. age, weight, height) will be summarized by descriptive statistics (n, mean, median, standard deviation, minimum and maximum).

Medical history

Medical history and ongoing conditions will be summarized and listed. The summaries will be presented by primary system organ class (SOC) and preferred term (PT). Medical history and current medical conditions will be coded using the Medical Dictionary for Regulatory Activities (MedDRA) terminology. The MedDRA version used for reporting will be specified in the CSR and as a footnote in the applicable tables/listings. History of surgical and other medical procedures and any prior hepatic findings at baseline will be listed using FAS.

Other baseline characteristics

Clinically significant abnormality in ECG (yes or no) along with ECG parameters (heart rate, PR, QT, QTcF and QRS), overall interpretation in audiometric test (normal or clinically significant or insignificant abnormality as per CRF), and interpretation in ocular exam (normal or clinically significant or insignificant abnormality) at baseline will be summarized and listed using FAS.

The following variables will be summarized as a continuous and categorical data using FAS, except for urine protein/creatinine ratio which will be presented as categorical data as shown below:

- Creatinine will be categorized as: \leq ULN, $>$ ULN - \leq 1.5*ULN, $>$ 1.5*ULN
- Recalculated Creatinine Clearance (CrCl) will be categorized as: $<$ 90 and \geq 90 mL/min
- ALT and AST will be categorized as: \leq ULN, $>$ ULN- \leq 2.5*ULN, $>$ 2.5*ULN
- Urine protein/creatinine ratio: \leq 0.5, $>$ 0.5
- Serum ferritin will be categorized as: \geq 1000 to 2500, \geq 2500 to 5000, $>$ 5000 ng/ mL

2.6 Treatments (study treatment and compliance)

2.6.1 Cumulative dose

The planned daily dose of a subject is collected on the CRF page as dose prescribed in mg/kg/day and the actual daily dose is calculated by dividing the total daily dose collected on the CRF page in mg by the current weight (kg) corresponding to that visit and based on the start and end dates. The current weight is equal to the weight on the same visit when dose was administered or the last available weight before the dosing visit if the same visit weight is missing. Cumulative dose (mg/kg) is defined as the sum over the daily doses of all days between first and last dose. For patients who did not take any drug, the cumulative dose is by definition equal to zero.

Cumulative dose = sum of (daily dose at a visit * (end date of dose - start date of dose +1))

The **planned cumulative dose (mg/kg)** for a study treatment component refers to the total planned dose as per the protocol up to the last date of investigational drug administration. The **actual cumulative dose (mg/kg)** refers to the total actual dose administered, over the duration for which the subject is on the study treatment as documented in the Dose Administration eCRF.

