6.1.1 Dosing regimen

The recommendations for deferasirox FCT daily dose for pediatric patients' age ≥ 2 to <6 years with transfusional iron overload are the same as for adult patients, i.e. based on the weight of the patient. Changes in weight of pediatric patients over time must be taken into account when calculating the dose.

In children with transfusional iron overload aged between 2 and 5 years, exposure is lower than in adults. This age group may, therefore, require higher doses than are necessary in adults. However, the initial dose should be the same as in adults, with close monitoring by the investigator, followed by individual titration.

Table 6-3 Dose and treatment schedule

Study treatments	Pharmaceutical form and route of administration	Dose	Frequency and/or Regimen
Crushed Deferasirox FCT	Film-coated tablets p.o	Minimum dose 3.5 mg/kg/day Targeted starting dose 14 mg/kg/day Maximum dose 28 mg/kg/day Dosage is ascertained by patient weight. Please refer to dose weight Table 6-1 for the recommended dose in mg/ kg/day	Once daily; all doses must be crushed prior to administration

Deferasirox FCT is for oral use. The full daily dose of one or more film-coated tablets must be crushed in the home environment and administered by sprinkling the full dose on to soft food (e.g., yogurt or apple sauce [pureed apple]). The dose must be immediately and completely consumed, and not stored for future use. The study medication should be taken once daily, preferably at the same time each day.

Subjects who have been established on other chelation therapy will perform a 5 day wash-out from the former medication details are provided in [Section 7.1.2](#).

The patient's daily dose will be rounded to the nearest whole tablet according to the available strengths of deferasirox FCT tablets (90 mg, 180 mg, and 360 mg). The appropriate daily dose will be calculated by the investigator based on the patient's actual body weight see [Table 6-1](#).

The investigator and/or designee will instruct the caregiver and patient to crush the study drug and then take the full daily dose of one or more film-coated as prescribed. Examples among others of an adequate method of crushing of the FCT may be between two pieces of wax paper with a rolling pin or with a commercially available pill crusher. All doses planned and prescribed to the patient, and all dose changes including reasons for change during the study must be recorded in the case report form(CRF).

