6.3.1.12 Gastrointestinal disturbances

Some basic recommendations, based on practical experience, can be made to guide investigators in managing subjects who experience diarrhea.

At the first sign of diarrhea, consider anti-diarrhea medication such as loperamide.

Remind the subject to discontinue any laxative preparations or stool softeners.

Eat small, frequent meals. Determine if the subject is lactose intolerant. Note that deferasirox FCT does not contain lactose. Remind the subject to drink an adequate amount of clear liquid per day.

Patients with GI symptoms (including abdominal pain, nausea, vomiting, and diarrhea) and/or patients who are unable to tolerate once a day study drug dosing, the following treatment management steps are recommended in the order specified below:

- Change the timing of study drug administration from morning to evening, and in addition, try using an anti-diarrheal agent for 2 days in case of diarrhea
- If symptoms still continue, try administering the daily dose as a split dose twice daily.

[figure not shown]
Once symptoms resolve, twice daily dosing should be switched back to once daily.

Do not split dose if only prescribing one tablet per day.

- Should the GI issues persist, study drug may be discontinued if the investigator believes it is in the best interest of the patient.

Table 6-4 Criteria for dose reduction / interruption and re-initiation of deferasirox treatment for adverse drug reactions

Recommended dose modifications for deferasirox	
Body weight	
Increase/decrease of weight by >10% compared to baseline weight or body weight at last dose adjustment due to change in patient's body weight	
Dose of study medication needs to be adapted using Deferasirox FCT Weight Dose Table
 
Dose adjustment needed for Weight changes >10% compared to baseline weight or if there is a change in patient's body weight since last dose adjustment.
 
Smaller variations in body weight (<10%) during study, do not require dose adjustments. In this case, baseline body weight can be used to calculate correct dose.

Investigations (Renal)	
Serum creatinine and/or creatinine clearance	
Single increase in serum creatinine $\geq 33\%$	Maintain dose level and repeat the assessment at next visit as clinically indicated

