2.6.3 Planned and actual dose intensity

Planned dose intensity (PDI) and actual **dose intensity** (DI) for subjects with non-zero duration of exposure are defined as follows:

PDI (mg/kg/day) = [planned cumulative dose during the time of exposure (mg/kg)]/Duration of exposure (days)

DI (mg/kg/day) = [actual cumulative dose during the time of exposure (mg/kg)]/Duration of exposure (days)

Relative dose intensity (RDI) is defined as follows:

$$\text{RDI (\%)} = (\text{DI (mg/kg/day)} / \text{PDI (mg/kg/day)}) * 100$$

Planned dose intensity, actual dose intensity and relative dose intensity (<70%, 70%-90% and >90%) will be summarized by means of descriptive statistics using Safety Set.

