2.6.4 Dose Change

‘Dose interrupted’, and ‘Dose change’ fields from the Dosage Administration CRF pages will be used to determine the dose reductions, dose interruptions. The corresponding fields ‘Reason for dose changed/dose interrupted’ will be used to summarize the reasons. Dose interruption and dose reduction are defined as follows:

- **Interruption** is defined as any period of zero actual daily dose prior to treatment end date.
- **Reduction** is a subset of the dose changes, defined as a decrease from the previous planned non-zero dose, even if this decrease has been directly preceded by an interruption. Patient has dose decrease or reduction at visit if the dose assignment at the visit will be nonzero and lower than the last available one before the visit and daily dose is nonzero at the visit. For example, in the sequence 14 mg/kg/day - 0 mg/kg/day - 7 mg/kg/day, the 7mg/kg/day dose will be counted as a reduction and in the sequence 14mg/kg/day - 7 mg/kg/day - 3.5 mg/kg/day, 3.5 mg/kg/day will be counted as two reductions.

The number and percentage of patients with dose interruption and/or dose reduction along with reasons for dose interruption/reduction will be summarized using the safety set. Dose increase will not be included in these summaries.

Listings of all doses of the study treatment along with dose reduction and dose interruption reasons will be produced using the Safety set.

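### Relative dose intensity sets tablet-rounded mg at current weight against what appears to be the nominal mg/kg level, so some children who take every tablet would be classed as 70-90%

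*SAP*

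**What the plan says.** SAP 2.6.1 sets the two halves of the ratio on different bases. For the plan: "The planned daily dose of a subject is collected on the CRF page as dose prescribed in mg/kg/day". The planned cumulative dose "refers to the total planned dose as per the protocol up to the last date of investigational drug administration". For what was taken: "the actual daily dose is calculated by dividing the total daily dose collected on the CRF page in mg by the current weight (kg", using the weight at the dosing visit or, if that is missing, the last one before it. SAP 2.6.3 divides each cumulative dose by days of exposure to give planned and actual dose intensity (PDI and DI), and takes RDI as DI over PDI. These, with "relative dose intensity (<70%, 70%-90% and >90%) will be summarized by means of descriptive statistics using Safety Set", are reported under a section headed study treatment and compliance.

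The protocol determines what the tablet mg can be. Under 6.1.1 the "daily dose will be rounded to the nearest whole tablet according to the available strengths of deferasirox FCT tablets". These strengths are 90, 180 and 360 mg, so every daily dose is a multiple of 90 mg. On growth, the body-weight row of Table 6-4 says: "Smaller variations in body weight (<10%) during study, do not require dose adjustments".

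The documents point two ways on whether the prescribed level is nominal. SAP 2.6.4 illustrates planned doses with nominal levels ("in the sequence 14 mg/kg/day - 0 mg/kg/day - 7 mg/kg/day"), and Protocol 6.1 still labels 270 mg at 17-22 kg as 14 mg/kg/day. But Protocol 6.1 also describes the closest available dose as the one that is prescribed.

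**The concern.** A ratio reported under compliance and cut at 70% and 90% will be read as the share of the planned dose that the child took. On the nominal reading, it also carries the gap between the calculated dose and the nearest tablet combination, and any weight gain since the tablets were chosen. In small children one 90 mg step is a large part of the daily dose. A child who takes everything can then appear under-dosed, and a child who misses doses can sometimes appear fully dosed. At stake is the RDI table in a safety study of at least 40 children, where readers will look to see whether the intended exposure was reached.

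**Working it through.** **Inputs.** Tablet mg by weight and level from Protocol Table 6-1; RDI definition and cut-points from SAP 2.6.1 and 2.6.3; no tablet change for weight changes under 10% from Table 6-4. Assumed: whole weights of 10-25 kg (16 values) as a plausible range for ages 2 to under 6, and the seven levels from 7 to 28 mg/kg/day. That gives 16 x 7 = 112 cells. The 3.5 level is left out because Table 6-1 offers no tablet for it below 19 kg.

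**The protocol's own example.** 20 kg x 14 mg/kg = 280 mg calculated; nearest available 270 mg. This reproduces. RDI with full intake is 270/280 = 96.4%. The documents state no RDI figure to compare with.

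**Formula, nominal reading.** RDI at full intake = 100 x tablet mg / (level x current weight). With partial intake, multiply by the share of doses taken.

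Single cells:
- 16 kg at 14: 180/224 = 80.4%
- 19 kg at 7: 90/133 = 67.7%
- 12 kg at 10.5: 90/126 = 71.4%
- 13 kg at 10.5: 180/136.5 = 131.9%
- 10 kg at 14: 180/140 = 128.6%

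All 112 cells, full intake:

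| Level (mg/kg/day) | At or below 90% (weights, kg) | Above 110% |
|---|---|---|
| 7 | 5 (15-19) | 6 |
| 10.5 | 5 (10-12, 20, 21) | 5 |
| 14 | 3 (15, 16, 22) | 4 |
| 17.5 | 3 (12, 18, 23) | 2 |
| 21 | 2 (10, 15) | 1 |
| 24.5 | 0 | 2 |
| 28 | 1 (11) | 0 |
| Total | 19 of 112 | 20 of 112 |

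Two cells are exact ties at 315 mg (18 kg at 17.5; 15 kg at 21). Table 6-1 gives 270 mg for both, so each scores 270/315 = 85.7% and is counted in the middle column.

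**Below 70%.** One cell: 19 kg at 7 mg/kg/day. At 14 mg/kg/day the minimum is 80.4%.

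**Growth with tablets unchanged.** Divide by the growth factor. At 14 mg/kg/day and +5%, the 14 kg and 21 kg cells go from 91.8% to 91.8/1.05, about 87.5%, and join 15, 16 and 22 kg: 5 of 16 at or below 90%. These are daily ratios at the later weight; RDI over the whole exposure would lie between the starting and later values.

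**Missed doses.** At 75% intake, RDI exceeds 90% only where the full-intake value exceeds 90/0.75 = 120%. That holds in 6 of 112 cells: 10, 20 and 21 kg at 7; 13 and 14 kg at 10.5; 10 kg at 14 (128.6% x 0.75 = 96.4%). This assumes that missed doses are recorded on the CRF.

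**Other reading.** If the CRF field holds the rounded dose as mg/kg at the prescribing weight, rounding drops out and only growth remains. At +10% the full-intake ratio is 1/1.10 = 90.9%, still in the top class.

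**The case against.** Several points on the other side stand.

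- Delivered mg/kg over target mg/kg is a legitimate exposure measure. A 19 kg child on 90 mg receives 90/19 = 4.7 mg/kg/day against a nominal 7, and a low ratio reports that truthfully. But PDI and DI, both in mg/kg/day, already show it, so RDI need not carry it as well.
- The nominal reading is an inference. The SAP never says the prescribed level is unrounded, and its 14, 7 and 3.5 examples are there to explain how reductions are counted. If the field holds the realised dose, the effect largely disappears. The SAP therefore has to say which is meant.
- Recorded missed periods are not lost. Interruptions and reductions are tabulated with reasons, all doses are listed (SAP 2.6.4), and compliance is assessed at each visit (Protocol 6.6.3.1).

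A reader might infer more: that adherent children will often be classed below 70%, that missed doses will generally be hidden, or that the GI event rate is distorted. The documents do not support these. The first occurs in one cell before growth. The second, at 75% intake, occurs in six, all just above a tablet step. As to the third, the primary analysis is a proportion with an exact interval and the supportive rate uses patient-time; neither uses RDI.

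**Conclusion.** The point holds on the nominal reading, which the wording favours but does not settle. The main error is placing fully adherent children in the 70-90% class: 19 of 112 cells at or below 90%, of which 18 lie in 70-90% and one below 70%. At 14 mg/kg/day, which Protocol Table 6-3 names as the targeted starting dose, it is 3 of 16 weights, rising to 5 of 16 after 5% growth. A further 20 of 112 cells exceed 110%.

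These are counts of cells over an assumed weight range, each weighted equally. The documents give no distribution of weights or dose levels, so 19 of 112 must not be read as a share of patients. What is distorted is the RDI table as a summary of exposure and compliance. The primary GI result stands as planned. Nothing here bears on which dose is appropriate.

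**What to change.** State in SAP 2.6.1 whether the prescribed mg/kg/day is the nominal level or the tablet-rounded dose. For RDI, define the planned daily dose as the prescribed tablet mg divided by the same weight used for the actual dose. Weight then cancels day by day: full intake gives 100% at every weight and level, and an even 75% intake gives 75%. Take prescribed mg from the CRF or, if it is not a field there, derive it from the level, the dosing weight and Table 6-1. Keep the PDI and DI summaries already specified in SAP 2.6.3, with PDI on the nominal level, so that delivered exposure against nominal remains visible.

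The cost is a few sentences in the SAP and a small programming change, with a derivation step if prescribed mg was not collected. The downside is that RDI alone would no longer show a shortfall from rounding or growth; readers would get that from PDI and DI. No dosing rule changes.
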